3.0 Inclusion and Exclusion Criteria

3.1 Screening for eligibility.

Recruitment. We will identify six PAD participants age 55 and older meeting eligibility criteria for our proposed pilot study. For this pilot study, we will contact six PAD patients who participated in our previous research studies and agreed to be contacted for future research studies conducted by [name].

PROTOCOL TITLE: Unacylated Ghrelin to Improve Functioning in PAD: the GIFT Trial

We may also use the Enterprise Data Warehouse to identify six consecutive patients with PAD to participate in this pilot study.

3.2 Criteria.

Inclusion Criteria. All participants will be age 55 and older. All will have an $ABI \leq 0.90$ at baseline. $ABI \leq 0.90$ is a well-accepted standard for defining PAD (44-47). In addition, people with a history of lower extremity revascularization for PAD will be eligible.

Exclusion Criteria.

1. Above or below-knee amputation, critical limb ischemia, and wheelchair confinement.
2. Cardiovascular event during the previous three months. [Note: Participants who have undergone coronary revascularization for a cardiac event during the previous three months may still qualify.]
3. Major medical illnesses including renal disease requiring dialysis, or cancer requiring treatment in the previous year.
4. Participation in another clinical trial or completion of a clinical trial in the previous month, unless they were in the control group of the previous trial.
5. Unwilling to attend nine study visits over approximately six months.
6. Surgery including lower extremity revascularization or orthopedic surgery in the previous month or anticipated surgery in the next three months.
7. Greater than 15 mmHg difference in blood pressure in both arm pressure measurements during the ABI, diagnosis of Raynaud's phenomenon, or unable to have the blood pressure checked in both arms.
8. Blood pressure $< 90/50$ at baseline.
9. Non-English speaking, a visual impairment that limits ability to read the consent, or a hearing impairment that interferes with study participation.
10. In addition to the above criteria, investigator discretion will be used to determine if the trial is unsafe or not a good fit for the potential participant.

3.3 Special Populations.

Vulnerable populations (fetuses, pregnant women, children, prisoners, and institutionalized persons) and adults unable to consent will not be included in this study.

4.0 Study-Wide Number of Subjects

NA

5.0 Study-Wide Recruitment Methods

NA

PROTOCOL TITLE: Unacylated Ghrelin to Improve Functioning in PAD: the GIFT Trial

6.0 Multi-Site Research

NA

7.0 Study Timelines

Each participant's part in this study will last up to approximately six months.

Visit 1.

The initial visit will last approximately 2 hours. Informed consent will be provided and an ankle brachial index (ABI) measurement will be obtained to ascertain eligibility. Questionnaires will be administered to obtain information about their health and medical history. The six-minute walk test and the four-meter walking velocity at usual and fastest pace may be obtained. An electrocardiogram (ECG) will be performed and a blood sample will be obtained. Blood will be tested for liver and kidney function, electrolytes, and a complete blood count (CBC). A physical exam will be performed and medical history will be obtained. Height and weight will be measured. Vitals may be obtained. Vitals include blood pressure, heart rate, respiratory rate, temperature, and oxygen level.

Visits 2, 5, and 8.

Visits 2, 5, and 8 will last approximately 8-12 hours and will be separated by at least one week. We plan to collect data for each dose on all six participants before proceeding to the next dose. At visits #2, #5, and #8, respectively, participants will receive a subcutaneous injection of unacylated ghrelin of the following doses:

Visit 2: 10ug/kg

Visit 5: 20 ug/kg

Visit 8: 40 ug/kg

Prior to the injection. Prior to the injection, blood will be drawn and measured for levels of unacylated ghrelin and acylated ghrelin, inflammatory biomarkers, liver and kidney function, electrolytes, and CBC. Blood pressure and pulse will be obtained seated and in the standing position. Brachial artery flow-mediated dilation (FMD) will be measured.

30 minutes, 60 minutes, 90 minutes, and 3 hours and 6 hours post-injection.

A blood sample will be obtained and measured for levels of unacylated ghrelin and acylated ghrelin. Blood pressure and pulse will be obtained seated and in the standing position. A brachial artery FMD may be measured at 6 hours (e.g. if we do not see a change in brachial artery FMD 8-12 hours post-injection, we may want to move the collection time point to 6 hours).

8-12 hours post-injection. A blood sample will be obtained and measured for levels of unacylated ghrelin and acylated ghrelin as well as inflammatory markers.

PROTOCOL TITLE: Unacylated Ghrelin to Improve Functioning in PAD: the GIFT Trial

Blood pressure and pulse will be obtained seated and in the standing position. Brachial artery FMD may be measured.

Additional vitals will be obtained at the discretion of the CRU nurse throughout the visit. Vitals include blood pressure, heart rate, respiratory rate, temperature, and oxygen level. Participants will be administered a questionnaire to assess symptoms. Participants may be asked to take their medications in the evening rather than the morning on the day of injection visits.

Participants may also be asked to repeat the six-minute walk and/or four-meter walks performed at baseline.

Visits 4 and 7.

At visits 4 and 7, a blood sample will be obtained and tested for liver and kidney function, electrolytes, and CBC. The physical exam and medical history may be repeated. Weight may be re-measured.

Visits 3, 6, and 9.

Visits 3, 6, and 9 will occur approximately 24 hours after the subcutaneous injections given at visits 2, 5, and 8, respectively. A blood sample will be obtained and measured for levels of unacylated ghrelin and acylated ghrelin as well as inflammatory markers and liver and kidney function, electrolytes, and CBC. Blood pressure and pulse will be obtained seated and in the standing position. Brachial artery FMD will be measured and an ECG will be performed. Vitals may be obtained at the discretion of the CRU nurse. Participants will be administered a questionnaire to assess symptoms.

Prior to FMD measures, the participant will be asked to consume a low calorie, low fat meal provided to the participant by CRU nutrition services.

The table below lists timing of the outcome and safety measures.

Measures	Prior to Injection *	30 minutes	60 minutes	90 minutes	3 hours	6 hours	8-12 hours	24 hours
Safety Measures								
Electrocardiogram	X*							X
Comprehensive chemistry panel	X*							X
CBC	X*							X
Pulse and blood pressure	X	X	X	X	X	X	X	X
Orthostatic pulse and blood pressure	X	X	X	X	X	X	X	X

PROTOCOL TITLE: Unacylated Ghrelin to Improve Functioning in PAD: the GIFT Trial

Efficacy outcome measures								
Unacylated and acylated ghrelin levels	X	X	X	X	X	X	X	X
Inflammatory biomarkers	X						X	X
Brachial artery FMD	X					X	X	X

*The ECG, comprehensive chemistry panel (liver and kidney function and electrolytes), and CBC will be obtained at visit #1 for the 10 ug/kg dose.

**The FMD will be performed at either 6 hours or 8-12 hours.

We will test doses of 10 ug/kg, 20 ug/kg, and 40 ug/kg of unacylated ghrelin on three separate days for each participant. These doses were selected based on published literature and the experience of our consultants [name], who has an ongoing study of intravenously administered unacylated ghrelin in healthy people (R01-DK097550) and [name], who has an ongoing study of subcutaneously administered acylated ghrelin in older frail people without PAD (R21-AG040488).

Justification for proposed doses of unacylated ghrelin. Unacylated ghrelin is a synthetic 28 amino-acid protein. The ½ life of intravenously administered unacylated ghrelin is 30-34 minutes, which is comparable to but slightly longer than the ½ life of insulin and glucagon (9). In comparison, the ½ life of intravenously administered acylated ghrelin is 9 to 11 minutes (9). A portion of intravenously administered acylated ghrelin is converted to unacylated ghrelin (9). In contrast, unacylated ghrelin is not converted to acylated ghrelin (9). In healthy people, circulating levels of unacylated ghrelin are higher than those of acylated ghrelin, in a ratio that is typically 4:1 but ranges from 2:1 to 9:1 (9,11,48). In a study of healthy people, a 4X higher dose of intravenously administered unacylated ghrelin achieved a CMax that was twelve times higher than that for intravenously administered acylated ghrelin (9). Because of the longer ½ life of unacylated ghrelin and the substantially greater CMax achieved with unacylated ghrelin as compared to acylated ghrelin, we will begin with a subcutaneous unacylated ghrelin (10 ug/kg) dose that is comparable to that selected by [name] for her study of subcutaneously administered acylated ghrelin. Next, we will test a subcutaneous dose of unacylated ghrelin that is 2X the starting dose (20 ug/kg). Finally, we will test a subcutaneous dose of unacylated ghrelin that is 4X times the starting dose (40 ug/kg). Four times the starting dose was selected as the maximal dose to test because circulating levels of unacylated ghrelin are approximately four times higher than circulating levels of acylated ghrelin and because of the higher CMax of unacylated as compared to acylated ghrelin (9,11,48). Although the GIFT Trial will administer unacylated ghrelin subcutaneously, we anticipate that, similar to intravenous administration, the maximum concentration of unacylated ghrelin will be greater than that for acylated ghrelin.

PROTOCOL TITLE: Unacylated Ghrelin to Improve Functioning in PAD: the GIFT Trial

We anticipate that we will enroll all study subjects within one year of obtaining IRB approval. We anticipate that we will complete data collection within thirteen months of obtaining IRB approval.

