9.0 Procedures Involved

9.1 Study design.

STUDY OVERVIEW. We will identify the lowest subcutaneous dose of unacylated ghrelin that maximizes brachial artery flow mediated dilation (FMD). These PAD participants will receive three different subcutaneous doses of unacylated ghrelin on three different days and will undergo measurement of unacylated ghrelin levels prior to the injection and at specified time intervals. Each dose will be separated by a wash-out period of \geq one week. Data will be obtained for all six participants at each dose before moving to the next dose. We will test doses of 10 ug/kg, 20 ug/kg, and 40 ug/kg of unacylated ghrelin on three separate days for each participant. These doses were selected based on published literature and the experience of our consultants [name], who has an ongoing study of intravenously administered unacylated ghrelin in healthy

PROTOCOL TITLE: Unacylated Ghrelin to Improve Functioning in PAD: the GIFT Trial

people (R01-DK097550) and [name], who has an ongoing study of subcutaneously administered acylated ghrelin in older frail people without PAD (R21-AG040488).

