Selecting the dose of unacylated ghrelin for future study. We will select the lowest subcutaneous dose of unacylated ghrelin that maximizes brachial artery FMD and minimizes circulating levels of oxidative stress. We will also use unacylated ghrelin levels to select the unacylated ghrelin dose. In selecting the dose, greater increases in brachial artery FMD and lower levels of oxidative stress will be prioritized over the level of unacylated ghrelin. For example, if the dose of 40 ug/kg results in substantially higher levels of unacylated ghrelin compared to the dose of 20 ug/kg, but improvement in brachial artery FMD is similar between the 20 ug/kg and the 40 ug/kg doses, then we will select a dose of 20 ug/kg for use in a possible future trial of unacylated ghrelin in PAD patients.

PROTOCOL TITLE: Unacylated Ghrelin to Improve Functioning in PAD: the GIFT Trial

9.2 Describe all research procedures.

Please see sections 7.0, 8.1, 8.2, and 9.1 above.

Ankle Brachial Index (ABI). After the participant rests supine for five minutes, the right brachial, dorsalis pedis (DP), posterior tibial (PT) and left DP, PT, and brachial artery pressures are measured using a hand-held Doppler probe. Pressures are measured twice. The ABI is calculated for each leg by dividing the average of the DP and PT pressures by the average brachial pressure.

Questionnaire Administration. Participants will be administered study questionnaires by a trained and certified health interviewer.

Brachial Artery Flow-Mediated Dilatation (FMD). Brachial artery imaging will be performed by a Registered Diagnostic Cardiac Sonographer according to established protocol (44,45). Changes in FMD will be read by [name] University of Wisconsin Atherosclerosis Imaging Research Program Core Laboratory by a single reader blinded to participant characteristics. We have more than a decade of experience working with [name] reading center (44,47,48). Measurement reproducibility in [name] laboratory has a median FMD difference of 0.02% (inter-quartile range: -0.03 to 0.04).

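### The injection-day FMD may be moved from 8-12 h to 6 h if no change is seen; with doses given in ascending blocks, a move would mix dose with time since injection

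*Combined protocol and SAP*

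**What the plan says.** Section 7.0 describes the 6 h and 8-12 h readings at the injection visits in permissive terms. For each, "brachial artery FMD may be measured". The example given for using 6 h instead depends on the result: "if we do not see a change in brachial artery FMD 8-12 hours post-injection, we may want to move the collection time point". The schedule table marks both columns, but its footnote says "The FMD will be performed at either 6 hours or 8-12 hours". At the 24 h visits the wording is firm: "Brachial artery FMD will be measured and an ECG will be performed".

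Other sections give the injection-day time differently. The Specific Aim in section 1.1 has roughly six to eight hours. Sections 8.1 and 14.0 have six or 8-12 hours.

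Dosing is in ascending blocks of 10, 20 and 40 ug/kg. Section 7.0 states: "We plan to collect data for each dose on all six participants before proceeding to the next dose". Section 9.1 repeats it: "Data will be obtained for all six participants at each dose before moving to the next dose".

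Section 9.1 selects the lowest dose that maximizes FMD. Its worked example turns on whether "improvement in brachial artery FMD is similar between the 20 ug/kg and the 40 ug/kg doses", and it adds that "greater increases in brachial artery FMD and lower levels of oxidative stress will be prioritized over the level of unacylated ghrelin". It does not say which FMD time is meant. Section 11.1 plans simple statistics and does not say how readings taken at different times would be handled.

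**The concern.** A dose comparison is interpretable only if the outcome is read at the same time after each dose. Here the time may change in response to the data, and the block order means a change would fall on later and therefore higher doses. The move would be to a time the team thinks more likely to show an effect. If 6 h does respond more than 8-12 h, the shift would look like the dose response hypothesized in section 1.2 and would work against choosing the lowest adequate dose.

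At stake is the study's main product, the dose for a possible later trial. Section 8.1 describes the FMD endpoint by the six or 8-12 h reading. Section 14.0 ties dose selection to FMD immediately after describing that same reading. Neither mentions the 24 h reading. The effect size and SD that section 11.1 hopes to estimate would also be blurred.

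**Working it through.** The plan has no power, effect-size or SD figure to reproduce.

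**1. Injection-day FMD time, side by side**

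| Place | Time given |
|---|---|
| 1.1 Specific Aim | about 6 to 8 h |
| 7.0 visit text | 6 h optional, 8-12 h optional, move allowed |
| 7.0 table | 6 h and 8-12 h both marked |
| 7.0 table footnote | one or the other |
| 8.1 and 14.0 | 6 or 8-12 h |

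None of these requires a common time across doses.

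**2. What a move does to the contrasts**

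Model: FMD change = participant + dose + time. There are 6 x 3 = 18 readings and 6 + 2 + 1 = 9 parameters. Let T be the mean at 6 h minus the mean at 8-12 h.

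- *Common time:* the time term drops out, and all three dose contrasts are free of T.
- *Move after the 10 ug/kg block:* the design has rank 8 of 9. The observed 20-10 difference is the dose effect plus T, and so is 40-10. Only 40-20 is clean.
- *Move after the 20 ug/kg block:* rank 8 of 9. The 40-10 and 40-20 contrasts carry T. Only 20-10 is clean.
- *Move after three of six participants at 10 ug/kg:* rank 9, so the contrasts are estimable, but only with adjustment for time. The unadjusted 10 ug/kg mean is off by T x 3/6.

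After a between-block move, no analysis of the injection-day readings can separate dose from time.

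**3. Illustrative size (all inputs assumed)**

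Simulation of 200,000 trials with n = 6, unit SD of FMD change, between-dose correlation 0 or 0.5, and no dose effect. The choice is the lowest dose whose mean lies within the margin of the best mean. No change is defined in three ways: mean at or below 0, two-sided p of at least 0.05, or no significant rise. It is checked after the 10 and again after the 20 ug/kg block. T = 0.5 SD. Entries are the chance that a dose above 10 ug/kg is chosen; ranges span both correlations and all three definitions.

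| Scenario | Margin 0.5 SD | Margin 0.25 SD |
|---|---|---|
| One common time | 18-30% | 41-48% |
| No effect at 8-12 h, always moves when no change is seen | 49-67% | 66-86% |
| No effect at 8-12 h, moves half of those times | 37-54% | 57-72% |
| 0.5 SD effect at 8-12 h, always moves when no change is seen | 25-65% | 46-82% |

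The chance of a move after the 10 ug/kg block is 50%, 95% and 97.5% under the three definitions with no 8-12 h effect. With a 0.5 SD effect it is 11%, 83% and 83%.

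Sensitivity at the 0.5 SD margin:

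- T = 0.25 SD, always moving: 34-48% with no 8-12 h effect, 22-48% with a 0.5 SD effect.
- T = 0: 18-30%, as at a common time.
- Within-block move, three of six read late: 0.5 x 3/6 = 0.25 SD false difference, 41-48%.
- Within-block move, two of six read late: 0.5 x 2/6 = 0.17 SD false difference, 32-42%.

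**4. Can the two times be presumed alike?**

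The gap between 6 h and 8-12 h is 2 to 6 hours. With the intravenous half-life of 30-34 minutes in section 7.0, that is 120/34 = 3.5 to 360/30 = 12 half-lives. Subcutaneous kinetics are unknown and FMD need not follow the level, so this shows only that equality cannot be taken for granted.

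**The case against.** The strongest reply is that the harm needs a chain of events, none of them planned. Results must come back from the outside core laboratory in time, the team must move, the move must straddle doses, the two times must truly differ, and unlike readings must then be compared. The wording is permissive throughout. This is also a six-person pilot of a route never before used in humans for this compound, so freedom over timing has real value; fixing one time risks making every injection-day reading uninformative. The 24 h FMD keeps the same nominal time at every dose, and oxidative stress and ghrelin levels also inform the choice.

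Most of this stands as a limit on weight. The percentages rest on assumed inputs. The highest need a trigger that fires 95-97.5% of the time and a team that always moves. With a 0.5 SD effect at 8-12 h and the mean-at-or-below-zero trigger, the figure is 25-35% against 18-30%, a small change. The rule is noisy with six participants even at a common time. It is also fair that 8-12 h is itself a four-hour window (240/34 = 7 to 240/30 = 8 intravenous half-lives), which the simulation treats as one time.

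It does not remove the point. The clause itself supposes that the 8-12 h result will be seen and that 6 h may differ. No section makes the 24 h reading the basis for comparing doses. Flexibility can be kept by measuring at both times.

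**Conclusion.** The concern holds and should be fixed. The plan permits a result-triggered change in when FMD is read, requires no common time, and uses a block order that would turn a between-block change into complete confounding of the dose contrasts spanning it. That part follows from the design and needs no assumed numbers.

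The effect on the dose choice is conditional on a move and on a real time difference. Under the main illustrative assumptions, the chance of wrongly passing over 10 ug/kg rises from 18-30% to 49-67%; with no time difference it does not change. The 24 h FMD, oxidative stress and ghrelin levels were not modelled and could dilute the effect. The severity rests on the loss of comparability, which cannot be undone once a block has been read at another time, and not on the simulated percentages.

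**What to change.** State that the FMD used for dose selection is taken at the same post-injection time for all participants and all three doses, and that doses are compared only on same-time readings. Then do one of the following:

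- Replace the clause allowing a move with a single named time. If the time is moved all the same, state that readings at different times will not be compared across doses and that the cross-dose FMD comparison will use the 24 h reading.
- Keep both times open by measuring FMD at 6 h and at 8-12 h at every dose, as the table columns already suggest. A narrower late window would help.

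Reconcile sections 1.1, 7.0 (text, table and footnote), 8.1 and 14.0, and name the FMD time in the section 9.1 selection rule.

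The common-time rule is wording only and adds no scan, visit or participant. Its price is less freedom to change the time mid-study: a single named time could prove uninformative, and so could the 24 h fallback if the effect has faded. Measuring at both times avoids the first risk for up to 6 x 3 = 18 extra scans within visits already planned at 8-12 hours. It would have to be fitted around the pre-FMD meal (section 7.0) and the optional walk tests at about four to eight hours (section 9.2). The fixed ascending order remains a separate limitation.

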8.0 Study Endpoints

8.1 Primary and secondary study endpoints.

We selected brachial artery FMD as an endpoint because unacylated ghrelin increases brachial artery FMD within hours of intravenously administered unacylated ghrelin (8). This immediate effect on brachial artery FMD provides a short-term therapeutic endpoint for identifying an optimal unacylated ghrelin dose. The brachial artery FMD will be measured at baseline and at six or 8-12 hours after each dose of unacylated ghrelin is administered.

Additional endpoints for this pilot study include a) circulating levels of unacylated ghrelin; b) levels of acylated ghrelin; c) biomarkers of inflammation.

8.2 Primary or secondary safety endpoints.

Unacylated ghrelin has been administered intravenously to more than 70 humans without any serious adverse effects (4,8-14). Two participants in one study experienced mild facial swelling after receiving unacylated ghrelin intravenously (14). Symptoms resolved within hours (14). Dizziness was reported in one study in which intravenous acylated and unacylated ghrelin were administered simultaneously over the short term (12). However, this adverse effect was not observed when unacylated ghrelin was administered alone (12). We will monitor participants for symptoms of facial swelling and dizziness. We will monitor participants for blood pressure and signs of facial swelling. An electrocardiogram will be obtained at visit 1 and before the 20 ug/kg and 40 ug/kg injections and 24 hours after each injection. Renal function, liver function, electrolytes, and CBC will be obtained at baseline, before the 20 ug/kg and 40 ug/kg injections, and approximately 24 hours after each injection.

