Minimizing risks related to unacylated ghrelin. The six participants who receive the three injections of increasing doses of unacylated ghrelin will be observed at Northwestern Medical Center for approximately 8-12 hours after each injection. Participants will be observed for side effects. Participants will also return at 24-hour follow-up for assessment. The three injections will be separated by intervals

PROTOCOL TITLE: Unacylated Ghrelin to Improve Functioning in PAD: the GIFT Trial

of at least one week. Safety will also be monitored by our data safety monitoring board (DSMB) (see below).

Minimizing risk related to baseline and follow-up testing. All study coordinators undergo baseline training and are certified by [name] before beginning data collection. Training and certification involves ensuring that coordinators are trained in methods to help minimize falls. [name] re-certifies coordinators every six months to ensure continued adherence to study protocol. Those who are not adhering to protocol undergo additional training followed by re-certification.

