Data and Safety Monitoring Board (DSMB). We have identified three individuals: [name], Professor of Medicine at University of Colorado, [name], Professor of Endocrinology at the University of Illinois at Chicago, and [name], Professor of Statistics, University of Illinois at Chicago who have agreed to serve on the DSMB for the GIFT Trial. [name] is an internationally recognized expert in vascular medicine and is a board-certified cardiologist. [name] is an internationally recognized expert in endocrinology and is board certified in endocrinology. [name] is an internationally recognized statistician with expertise and experience with clinical trials and also missing data. All have provided letters of support, agreeing to

PROTOCOL TITLE: Unacylated Ghrelin to Improve Functioning in PAD: the GIFT Trial

participate in the GIFT Trial. The DSMB held their first meeting by telephone conference on Monday June 27, 2016. The DSMB will meet at least every six months during the study or more frequently as requested by the DSMB. The DSMB will convene by telephone conference call to review and approve the protocol prior to beginning data collection. The biostatisticians and data manager will work closely with the DSMB to perform interim analyses. Adverse events will be monitored continuously throughout the study and will be reported to the DSMB and IRB in a timely manner according to pre-specified requirements. Adverse event rates and interim study results will be reviewed and discussed by the DSMB at their regularly scheduled meetings. At least four categories of adverse events will be defined: a) Death; b) cardiovascular events (myocardial infarction, stroke, and coronary arrhythmias) c) lightheadedness/dizziness; d) swelling. We will report all hospitalizations to the DSMB in a timely fashion. We will use a designated data collection form to record these events and they will be reported to the Institutional Review Board according to local IRB requirements. They will be reported to the DSMB as required by the DSMB charter. As noted above, however, to date unacylated ghrelin has been found to have little to no toxicity in humans.

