12.0 Provisions to Monitor the Data to Ensure the Safety of Subjects

Serious adverse events will be reported to the DSMB within seven days of each serious adverse event. Adverse event data will be reported to the DSMB every six months during the study, and/or as requested by the DSMB. The DSMB will have the ability to stop the study at any time if there are concerns about safety.

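### No contact is scheduled after visit 9, about 24 hours after the 40 ug/kg injection, so delayed adverse events at the highest dose would surface only if the participant reports them (minor; cheap to fix)

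*Combined protocol and SAP*

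**What the plan says.** Section 7.0 sets the three doses at visits 2, 5 and 8 (10, 20 and 40 ug/kg): "Visits 2, 5, and 8 will last approximately 8-12 hours and will be separated by at least one week". The next-day visits are fixed as follows: "Visits 3, 6, and 9 will occur approximately 24 hours after the subcutaneous injections given at visits 2, 5, and 8, respectively". Section 3.2 counts nine visits in all, so visit 9 is the last. The measures table in section 7.0 ends at 24 hours. Section 9.3 describes 8-12 hours of observation and adds: "Participants will also return at 24-hour follow-up for assessment".

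Between doses, visits 4 and 7 include safety labs (chemistry and blood count), while for the clinical part "The physical exam and medical history may be repeated". Before injection at visits 5 and 8, the same labs and seated and standing blood pressure and pulse are taken. Section 7.0 also requires a symptom questionnaire at visits 2, 5 and 8, without saying when in the day it is given or what period it covers. On ECGs, section 8.2 says: "An electrocardiogram will be obtained at visit 1 and before the 20 ug/kg and 40 ug/kg injections and 24 hours after each injection".

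On adverse events, the DSMB text in section 9.3 says: "Adverse events will be monitored continuously throughout the study". Section 12.0 says: "Serious adverse events will be reported to the DSMB within seven days of each serious adverse event". Neither gives an end date for collection or a method for finding events after visit 9.

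**The concern.** Up to 24 hours, the planned safety measures are the same at all three doses. After that they differ, and the difference runs against the dose with the least prior safety experience. A continuing participant is seen again after 10 and after 20 ug/kg. After 40 ug/kg nothing further is scheduled.

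The commitment to continuous monitoring does not say how an event would come to light once visits have stopped. The seven-day rule in section 12.0 governs how fast a known serious event is passed on; it does not find events. What remains is the participant's own initiative: section 9.3 supplies telephone numbers, and section 26.0 asks participants to contact the investigator if they need care.

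At stake is the completeness of the safety record at the top dose. Specific Aim 2 is the safety of increasing doses, section 1.1 says the drug has never been given subcutaneously to humans, and section 14.0 expects an average age of about 76 with frequent comorbidity. The event categories in section 9.3 (death, cardiovascular events, dizziness, swelling, and also hospitalizations) are not confined to the first day. Under section 13.0 a replacement starts at the dose the withdrawn participant would have had next. Someone entering at 40 ug/kg would therefore have all scheduled follow-up end about 24 hours after a first exposure.

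**Working it through.** The plan gives no figure to reproduce on this point, so the check is a count from the visit schedule, plus some context.

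**1. Guaranteed assessments later than the 24-hour visit, per completing participant** (section 7.0)

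| | after 10 ug/kg | after 20 ug/kg | after 40 ug/kg |
|---|---|---|---|
| Safety labs | visits 4 and 5 = 2 | visits 7 and 8 = 2 | 0 |
| Blood pressure and pulse | visit 5 = 1 | visit 8 = 1 | 0 |
| Symptom questionnaire | visit 5, coverage not stated | visit 8, coverage not stated | none |

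Visits 4 and 7 have no stated day. They are placed after visits 3 and 6 by visit order. The optional history and exam at those visits are not counted. The ECGs before 20 and 40 ug/kg are not counted either, because their day is not given.

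**2. Times six completers**

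- Labs: 2 × 6 / 2 × 6 / 0 = 12 / 12 / 0.
- Blood pressure and pulse: 1 × 6 / 1 × 6 / 0 = 6 / 6 / 0.
- Symptom questionnaire: present / present / none.

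If the draws at visits 4 and 7 were meant to serve as the pre-injection labs for visits 5 and 8, the lab count would be 6 / 6 / 0. The entry for 40 ug/kg is zero either way.

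**3. Is drug likely to be present after visit 9?** Section 7.0 says the "life of intravenously administered unacylated ghrelin is 30-34 minutes". Half-lives in 24 hours are 1440/34 = 42.4 to 1440/30 = 48.0. No subcutaneous half-life is given. Assuming 1, 2 or 4 hours, 24 hours is 24, 12 or 6 half-lives, and at 4 hours the fraction left is 2^-6 = 1.6%. On these assumptions the gap concerns delayed events, not continuing exposure.

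**4. What one missed event would change.** With 0 of 6 events, the one-sided 95% upper bound is 1 − 0.05^(1/6) = 39%. With 1 of 6, the bound solves (1 − p)^5 (1 + 5p) = 0.05, giving p = 58%.

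**5. When should a closing call fall?** Take the injection at visit 8 as day 0 and visit 9 as day 1. A call on day 7 finds any event that began after visit 9 when it is at most 7 − 1 = 6 days old, inside the seven-day limit of section 12.0. On day 8 the maximum is 7 days, which leaves only same-day reporting.

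**The case against.** The strongest case against acting is that little is likely to be missed. Each injection is a single dose, and 24 hours spans more than 40 intravenous half-lives. The effects in section 8.2 are acute: mild facial swelling that cleared within hours, and dizziness seen only when both forms of ghrelin were given together. Nothing in the documents points to delayed toxicity, and no dose follows 40 ug/kg, so a late event could not alter a later escalation. The IND is in place, the DSMB must approve the protocol before data collection, and participants have direct telephone numbers. Methods of finding late events may also sit in the DSMB charter, the data collection forms, or the parts not available for review (text under Potential Risks in section 14.0, and section 20.0). All of this stands. It makes the point minor but does not supply a contact after visit 9.

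A second objection is that the measurements at visits 5 and 8 are baselines for the next dose, not planned late follow-up of the previous one. That is a fair description of their purpose. They still bring the participant back to the site, where a problem can surface, and 40 ug/kg has no counterpart.

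A reader might also infer that no dose has any late symptom check. The documents do not support that: section 7.0 requires a symptom questionnaire at visits 5 and 8, each at least a week after the preceding injection. Whether it precedes the new injection and looks back to the old one is unknown, so it can be counted neither as full coverage nor as none.

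**Conclusion.** The point holds as a minor one. In the available text, scheduled safety contact ends about 24 hours after the highest dose, while both lower doses have later visits. The imbalance is 12 / 12 / 0 for labs, 6 / 6 / 0 for blood pressure and pulse, and present / present / none for the symptom questionnaire. These counts assume six participants who complete all three doses, visits 4 and 7 falling in numerical order, and a literal reading of the pre-injection blood draw at visits 5 and 8.

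Two stronger readings are tempting and not supported. One is that the safety aim or the choice of dose is compromised: the 0-24 hour measures are the same at each dose, and the selection rule in section 9.1 rests on flow-mediated dilation, oxidative stress and ghrelin levels, none of which depends on contact after visit 9. The other is that delayed harm at 40 ug/kg is to be expected: the documents give no evidence of it, and the known kinetics, though intravenous only, point the other way. What remains is a small gap that is cheap to close in a first subcutaneous study with safety as an aim.

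**What to change.** In section 7.0:

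- Add one closing safety telephone call about 7 days after visit 8, using the existing symptom questionnaire and adverse-event form with onset dates. Day 7 is preferable to day 8 because it leaves a day for reporting within the section 12.0 limit.
- State that adverse-event collection runs to that call.
- At visits 5 and 8, give the existing symptom questionnaire before injection and ask about onset since the previous dose.
- Summarise labs, ECG, blood pressure and pulse by dose on the common 0-24 hour window.

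The report should not claim equal recall across doses. The interval between injections is only a minimum of one week, and all six participants finish a dose before the next begins, so visits 5 and 8 may fall well beyond day 7. Onset dates allow symptoms to be cut to a common period but do not equalise memory.

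The cost is six short calls, a questionnaire at visits already on site, a few sentences of text, and about one more week of participation. Doses, injection intervals and sample size do not change. Late labs, blood pressure and pulse stay unequal across doses, since a call cannot supply them.
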